15.2.2 Adverse Events Leading to Study Intervention Discontinuation

Population: SAF analysis set

An overview table of adverse events leading to discontinuation or dose reduction will be provided, by dose level and overall, summarizing the number and percentage of participants with any:

- TEAE leading to temporary discontinuation of at least one trial treatment, all trial treatments, peposertib (regardless of other trial treatments status), RT (regardless of other trial treatments status), capecitabine (regardless of other trial treatments status) (corresponding to AEs with action taken = “Drug interrupted” for peposertib, RT or capecitabine)
- TEAE leading to permanent discontinuation of at least one study intervention, all trial treatments, peposertib (regardless of other trial treatments status), RT (regardless of other trial treatments status) or capecitabine (regardless of other trial treatment) (corresponding to AEs with action taken = “Drug withdrawn” for peposertib, RT or capecitabine respectively)

The following frequency tables will be produced for each dose level and overall, by SOC and PT in alphabetical order:

- TEAEs leading to temporary discontinuation of at least one trial treatment
- TEAEs leading to temporary discontinuation of peposertib (regardless of other trial treatments status)
- TEAEs leading to temporary discontinuation of RT (regardless of other trial treatments status)
- TEAEs leading to temporary discontinuation of capecitabine (regardless of other trial treatments status)
- TEAEs leading to permanent discontinuation of at least one trial treatment

- TEAEs leading to permanent discontinuation of peposertib (regardless of other trial treatments status)
- TEAEs leading to permanent discontinuation of RT (regardless of other trial treatments status)
- TEAEs leading to permanent discontinuation of capecitabine (regardless of other trial treatments status)
- TEAEs leading to a delay in dose time of RT

15.2.3 Late Toxicities

A number of outputs will be produced for late adverse events. An adverse event is defined as a late toxicity if it starts after the on-treatment period, and it meets one of the following criteria:

- It is the first occurrence of adverse event for this participant on MedDRA preferred term level
- It is a recurring adverse event but there is gap between the end date of the previous occurrence and the start date of the re-occurrence (start date of re-occurrence – end date of previous occurrence > 0)
- It is a recurring adverse event and there is no gap between the end date of the previous occurrence and the start date of the re-occurrence, and the grade has worsened.

The following outputs will be produced for late toxicities:

- Table of all late toxicities by worst CTCAE grades: any grade (including AEs with missing grade), grades ≥ 3 , ≥ 4 and 5
- Listing of all late toxicities related to any trial treatment
- Listing of all late toxicities grade ≥ 3

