To assess the pharmacokinetics (PK) of peposertib	Pharmacokinetic profile of peposertib in terms of PK parameter estimates (e.g. C_{max} , AUC_{0-t} , t_{max} , CL/f , Vz/f , and $t_{1/2}$)	Fraction day (FD)1 and FD9

Overall Design: This is a multicenter, open-label, single arm, dose escalation study in participants with locally advanced rectal cancer.

The study will consist of a Screening period of 4 weeks, a Treatment period of 5 to 5.5 weeks (25 or 28 FD) (DLT period), a Short-term Safety Follow-up period of 13.5 weeks (including 30 days after surgery), a Long-term Safety Follow-up period until 1 year after the start of study intervention/randomization.

Number of Participants: The planned cohort size is 3 participants. The total sample size will depend on the number of cohorts to be evaluated. It is anticipated that 18 to 30 evaluable participants will be required.

Study Intervention Groups and Duration: Participants will be assigned to peposertib given in combination with capecitabine 825 mg/m² twice daily 5 days/week and RT of 50 to 50.4 Gy to the tumor area and 45 Gy to the electively irradiated tissues in 25 or 28 fractions (corresponding to 5 to 5.5 weeks). The starting dose of peposertib for the first cohort will be 50 mg once daily 5 days/week. The peposertib dose for the next cohorts will be determined by the Safety Monitoring Committee (SMC) guided by a Bayesian 2-parameter logistic regression model with overdose control.

[figure not shown]
Premature Discontinuation: As of 06 May 2021, in the Phase Ib dose escalation part, 19 participants have been treated with doses ranging from 50 to 250 mg peposertib once daily plus capecitabine and RT. Preliminary clinical data from 16 participants that have finished the study up to Week 19 as well as changing treatment landscape in locally advanced rectal cancer indicate that the ability to generate a meaningful proof of concept under the current protocol is low. Therefore, the dose escalation in the Phase Ib part will be prematurely discontinued after completing the Cohort 5 of 150 mg, and the Phase II part of the study will not be initiated.

Involvement of Special Committee(s): Yes

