In this study, appropriate precautionary measures to mitigate the potential risks are implemented. The safety will be monitored on an ongoing basis by the SMC. The study will be discontinued in the event of any new findings that indicate a relevant deterioration of the benefit-risk balance for the participants, which would render continuation of the study unjustifiable.

The SoC CRT has a known and well-established toxicity profile. Nausea, vomiting, diarrhea, mucositis, hand-foot syndrome, radiation dermatitis, and decreases in hemoglobin, leucocytes, and platelets, are the most frequently reported Grade 3 AEs in clinical studies with capecitabine and RT (Liu 2016). These potential toxicities can be readily monitored with clinical laboratory, AE, and clinical assessments.

It is known that RT can cause acute toxicities in the form of, e.g. radiation dermatitis and mucositis. Late toxicities arising 3 months or later after the end of RT can be seen in the form of, e.g. mucositis, fibrosis, and bowel perforation. This must be evaluated by appropriate means including physical examination, imaging and endoscopy when indicated. Potentially, acute and late toxicities can be more severe when RT is given in combination with peposertib. This will be evaluated on an ongoing basis.

Based on the available nonclinical and clinical data to date, the conduct of the study, as specified in this protocol, is considered justifiable.

The starting dose of 50 mg once daily peposertib in combination with RT and capecitabine is considered appropriate to mitigate possible AEs by overlapping or unexpected toxicities of the combination, and possible higher formulation-dependent fraction absorbed.

Peosertib has a nonclinical safety profile adequate for the treatment of patients with life-threatening advanced malignancies, and the safety profile does not raise concerns about further investigation of peposertib in participants with cancer. In addition, the available clinical safety data for peposertib when given as a single agent forms a basis for the clinical study in combination with RT, as well as chemotherapy, and supports the investigation also in the neoadjuvant setting.

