4.1.3 Follow-up Periods

The study follow-up will include:

- **Short-term Safety Follow-up:** the duration of the Short-term Safety Follow-up is approximately 13.5 to 14 weeks after treatment completion, including 30 days after surgery, with an optional 1 visit per week from Week 7 to Week 14 in case of acute toxicities until recovery to Grade 1 or to baseline. For all participants, a mandatory visit will be performed at Week 14, approximately 1 to 2 weeks prior to surgery, including a tumor assessment with MRI (T_2 weighted and diffusion weighted) needed for restaging and evaluation. Additional details on tumor evaluation methods and response assessments are provided in Section 8.1.2.
- Surgical intervention must be performed 15 weeks (\pm 14 days) after start of study intervention/randomization (i.e. approximately 9.5 weeks after stopping RT), unless there are contraindications for surgery, or if the participant refuses. The last Short-term Safety Follow-up visit is scheduled for Week 19, approximately 4 to 6 weeks after surgical intervention/imaging/biopsy, as per SoC. During this visit, all safety information since the last visit, including surgical and/or biopsy morbidities/toxicities will be collected.
- **Long-term Safety Follow-up:** participants will be followed-up at 21 and 27 weeks after start of study intervention/randomization; every 3 months until 1 year after start of study intervention/randomization. Details on tumor evaluation methods and response assessments are provided in Section 8.1.2. Adjuvant chemotherapy is allowed as per local standards (see Section 6.5). Participants receiving adjuvant chemotherapy will continue to follow the schedule of activities (SoA) as per protocol. If adjuvant chemotherapy is given, any additional safety evaluations/laboratory tests will be as per local practice.
- Participants who have already been followed up for more than 1 year (Long-term Safety or Survival Follow-up) will be discontinued from the study after the approval of protocol amendment version 4.0 by the respective Health Authority and Ethics Boards. Participants will be informed of the discontinuation by the Investigator via a phone call. No further study visits or assessments are planned.

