4.2 Scientific Rationale for Study Design

Study Interventions:

- In this study, peposertib will be used in combination with capecitabine and RT. Peposertib is a potent and selective, ATP-competitive inhibitor of DNA-PK and blocks a major DSB repair pathway (nonhomologous end joining pathway). Inhibitors of DNA-PK are expected to synergistically enhance the therapeutic effect of DSB-inducing anticancer modalities.
- The current SoC for locally advanced rectal cancer is capecitabine, a prodrug of 5-fluorouracil (5FU), in combination with RT (NCCN 2019, [Glynn-Jones 2017](#)). The mechanism of 5FU cytotoxicity has been attributed to the mis-incorporation of fluoronucleotides into RNA and

DNA and to the inhibition of the nucleotide synthetic enzyme thymidylate synthase which is responsible for the de novo synthesis of DNA (Longley 2003).

- The combination of peposertib with RT and 5FU showed improved antitumor activity and progression-free survival compared with RT + 5FU alone, in the HCT116 colorectal cancer xenograft model (please refer to the Investigator’s Brochure for further details).

Study Population:

- The inclusion and exclusion criteria (provided in Section 5.1 and Section 5.2, respectively) were chosen to maximize participant safety and possible potential benefit from peposertib in combination with capecitabine and RT.

Endpoint Selection:

- The aim of the study is to establish the MTD and RP2D of peposertib when given in combination with capecitabine and RT; therefore, the primary endpoint chosen is the occurrence of DLTs, which is a globally accepted endpoint for similar studies.

[figure not shown]

Interval to Surgery:

- Studies suggest that pCR rates when neoadjuvant CRT is administered in rectal cancer improve when the interval between the end of CRT and surgery ranges between 7 to 12 weeks (Ferrari 2015, Tulchinsky 2008, Kalady 2009, Zeng 2014, Roxburgh 2018). Therefore, in the current study, surgery is planned at approximately 9.5 to 10 weeks after the end of CRT.

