8.3 Adverse Events and Serious Adverse Events

The definitions of an AE and a serious adverse event (SAE) are in [Appendix 7](#).

8.3.1 Time Period and Frequency for Collecting Adverse Event and Serious Adverse Event Information

The AE reporting period for safety surveillance begins when the participant is initially included in the study (date of first signature of informed consent/date of first signature of first informed consent) and continues until the final assessment at 1 year. Any AE assessed as not related to study intervention will be recorded only up to the short-term safety follow-up period. Any AE assessed as related to study intervention will be recorded up to resolution or permanent outcome, irrespective of the time elapsed since the last administration of study intervention.

Any SAE assessed as related to study intervention must be recorded and reported, as indicated in [Appendix 7](#), whenever it occurs, irrespective of the time elapsed since the last administration of study intervention. Any SAE assessed as not related to study intervention must be recorded and reported, as indicated in [Appendix 7](#), only up to Week 27 in the long-term safety follow-up period.

The method of recording, evaluating, and assessing causality of AEs (including SAEs) and the procedures for completing and transmitting SAE reports are in [Appendix 7](#).

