Percent change from baseline: $100 * (visit value - baseline value) / baseline value$

Definition of on treatment period:

On treatment period is defined as the time from the first administration of study intervention to the last administration of study treatment + 30 days, or the clinical cut-off date (if the treatment is still ongoing), or death, whichever occurs first.

Date of last known to be alive

The date of last known to be alive will be derived for participants not known to be dead at the analysis cut-off using the latest complete date among the following:

- All subject assessment dates:

- Laboratory assessments using information from “Hematology”, “Biochemistry”, “Coagulation”, “Urinalysis”, “Pregnancy test” and “Creatinine Clearance” eCRF pages (LBDTC variable from LB SDTM domain to be used)
- Vital signs using information from “Vital signs” eCRF page (VSDTC variable from VS SDTM domain to be used)
- Performance status using “ECOG Performance status” eCRF page (QSDTC variable from QS SDTM domain to be used)
- ECG, using information from both local and central ECGS (EGDTC variable from EG SDTM domain to be used)
- Tumor assessments using “Tumor assessments” eCRF pages (TRDTC/TUDTC variable from TR/TU SDTM domain to be used)
- Surgery information using “Rectal Surgery at week 15”, “Rectal Surgery after Week 15”, “Surgery after discontinuation” eCRF pages
- Anti-cancer treatment after discontinuation start and end date from “Anti-Cancer treatment after discontinuation” eCRF page.
- Start dates of concomitant medications or anti-cancer therapies administered after study treatment termination using “Concomitant medications”, “Anti-cancer treatment after discontinuation details” eCRF pages (CMSTDTC variable from CM SDTM domain to be used)
- AE start dates from “Adverse events details” eCRF page (AESTDTC variable from AE SDTM domain to be used)
- Study treatment administration dates using “M3814 (PEPOSERTIB)/PLACEBO Administration Details”, “RT Administration” and “Capecitabine Administration” eCRF pages (EXSTDTC variable from EX SDTM domain to be used)
- Last known to be alive date using “Survival Follow-up page” (SSDTC variable from SS SDTM domain where SSCAT=“SURVIVAL FOLLOW-UP”), where status is “Alive”.

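### The SAP's late-toxicity window opens about two months before the protocol's description of late RT toxicity and takes in all protocol-timed surgery, so the only late-toxicity table can mix perioperative events with late radiation effects

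*SAP*

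**What the plan says.** SAP Section 15.2.3 gives the rule: "An adverse event is defined as a late toxicity if it starts after the on-treatment period". The event must also be new for that participant at preferred-term level, recur after a gap, or recur without a gap at a worse grade. SAP Section 9 closes the on-treatment period at "the last administration of study treatment + 30 days", or earlier at death or at cut-off if treatment is ongoing.

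Three outputs follow: one table of all late toxicities by worst grade, a listing of those related to any trial treatment, and a listing of those of Grade 3 or higher. The table has no restriction on relatedness or on surgery. By the SAP Section 9 default it is shown by dose level and overall.

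The protocol speaks of late toxicity in Section 2.3: "Late toxicities arising 3 months or later after the end of RT can be seen in the form of" mucositis, fibrosis and bowel perforation, among others. Section 4.1.3 places surgery at 15 weeks ± 14 days after treatment start, "approximately 9.5 weeks after stopping RT".

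On recording, protocol Section 8.3.1 states: "Any AE assessed as not related to study intervention will be recorded only up to the short-term safety follow-up period". Unrelated SAEs are recorded to Week 27, and related events throughout. The Schedule of Activities has surgical and postsurgical AEs collected at the Week 19 visit.

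The one surgery-specific AE output, in SAP Section 15.2.1, lists events within 6 weeks after surgery but is restricted to TEAEs. Under SAP Section 15.2, TEAEs must start within the on-treatment period.

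**The concern.** Version 4.0 of the protocol keeps follow-up to 1 year so that late RT toxicity can be seen, and Section 2.3 warns that such toxicity could be more severe with peposertib. The late-toxicity table is the summary a reader will turn to for that question.

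As defined, it can hold three kinds of event under one label: new events soon after treatment, complications of surgery of any cause, and late radiation effects. The protocol itself still offers visits for acute toxicity up to Week 14, well after the SAP has begun to call new events late.

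A participant spared surgery because of cCR (allowed under Surgery in protocol Section 8) cannot contribute an operative event. A difference between dose levels in the table's totals may therefore reflect who was operated on. Recording rules also change inside the window, so early and later parts of the same total are not ascertained alike.

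**Working it through.** **The plan's own figure.** Week 15 minus 5.5 weeks of treatment is 9.5 weeks, and Week 15 minus 5 weeks is 10 weeks. This reproduces protocol Section 4.2: "surgery is planned at approximately 9.5 to 10 weeks after the end of CRT".

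**Inputs.** Fractions: 25 or 28, five per week (protocol Section 4.1.2 and the Schedule of Activities). On-treatment period: last dose + 30 days (SAP Section 9). Three months: 3 × 30.4375 = 91.3, taken as 91 days, using the SAP Section 9 conversion. Surgery: 15 × 7 = 105, ± 14 = 91 to 119 (92 to 120 if the start day is counted as day 1). Assumption: FD1 is a Monday and no day is missed.

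| Study day | 25 fractions | 28 fractions |
|---|---|---|
| Last fraction | 33 | 38 |
| On-treatment period ends (+30) | 63 | 68 |
| SAP late window opens (+31) | 64 | 69 |
| 3 months after last RT (+91) | 124 | 129 |
| Surgery window | 91–119 | 91–119 |
| Surgery minus on-treatment end | 28 to 56 | 23 to 51 |
| 3-month point minus surgery | 5 to 33 | 10 to 38 |

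The two starting points differ by 91 − 30 = 61 days. Counting surgery as days 92 to 120 moves the last two rows by one day and changes nothing else.

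**Sensitivity.** With the maximum 7-day RT delay, surgery is 21 to 49 days (25 fractions) or 16 to 44 days (28 fractions) after the on-treatment period ends, and 12 to 40 or 17 to 45 days before the 3-month point. Every protocol-timed operation still lies between the two.

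**Recording.** All-cause recording runs to about Week 19 (19 × 7 = day 133). From the end of the on-treatment period that is 133 − 63 = 70 or 133 − 68 = 65 days. Of these, 61 precede the 3-month point: 61/70 = 87% or 61/65 = 94%. Afterwards only related AEs are recorded, plus unrelated SAEs to Week 27.

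**The surgery listing.** TEAEs must start by day 63 or 68 (day 70 or 75 with a 7-day delay), and surgery is on day 91 at the earliest. After a completed course and on-schedule surgery, the listing is empty.

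**What a 3-month cut would do.** For surgery on day 105, 124 − 105 = 19 or 129 − 105 = 24 of the first 30 postoperative days precede the cut (63% or 80%). For surgery on day 91 all 30 do. For surgery on day 119 only 5 or 10 do (17% or 33%), leaving 20 to 25 days inside the late window. The cut alone does not isolate surgical events.

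**Granularity.** With the planned cohort of 3, one participant moves a dose-level total by 1/3, or 33 percentage points.

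**The case against.** The strongest reply is that there is no clash between two analysis definitions. The 3 months is clinical description in the benefit/risk section. Protocol Section 9.4.2 defines no late-toxicity window, and the amendment rationale speaks only of toxicities developing within the first year. The SAP is free to set a catch-all for events after the TEAE window, and all-causality counting is defensible where attribution in irradiated, operated tissue is difficult. This stands. The problem is what the label leads a reader to conclude, not a breach of the protocol.

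Individual data also soften the point. The all-AE listing gives onset, last RT date and relatedness, and the disposition listing gives the surgery flag and date. In a small, exploratory study with no formal tests, listings carry much of the interpretation. They do not repair the table, however, and the related-events listing uses the same 30-day start.

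Three stronger readings should be set aside:

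- A reader might infer that surgical complications dominate the table. The documents show that they are eligible and collected, but give no counts.
- A reader might infer that a signal for fibrosis or perforation is diluted. If the table follows the organ-class and preferred-term layout of SAP Section 15.2, each term keeps its own row, and the denominator is the analysis set. Only any-event and organ-class totals are mixed.
- A reader might infer that data after Week 19 are related-only. Unrelated SAEs are recorded to Week 27.

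SAP Section 18.2 cites an external Clavien-Dindo term file. The visible SAP text describes no output that uses it, and its content cannot be judged here.

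**Conclusion.** The concern holds as a matter of definition and presentation in a supportive descriptive table. The SAP window opens 61 days before the protocol's description of late RT toxicity, and all protocol-timed surgery falls in between, with or without the maximum 7-day RT delay. Any-event and organ-class totals by dose level therefore partly reflect who had surgery, and they combine two recording rules. The output intended for perioperative events cannot catch them on schedule.

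The calendar result rests on a Monday start, five fractions per week, a completed course and surgery within its window. The claim about totals rests on the table following the general AE layout. How far the totals would shift cannot be stated from the documents. The primary DLT analysis is not affected.

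**What to change.** In SAP Section 15.2.3, replace the single table with two sets, each by dose level and worst grade and including Grade 3 or higher:

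- (a) post-treatment/perioperative AEs, with onset from day 31 after last dose to less than 3 months after last RT;
- (b) late toxicities, with onset 3 months or more after last RT.

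Show (b) twice: for events related to any trial treatment, which are recorded throughout, and for all causality. Footnote the all-causality version with the recording limits (unrelated AEs to the end of short-term follow-up, unrelated SAEs to Week 27). Flag events within 6 weeks after surgery in both sets, because the 3-month cut does not remove complications of operations late in the window.

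In SAP Section 15.2.1, change the surgery listing from TEAEs to all AEs.

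The cost is a wording change and one or two extra tables. AE onset, last RT date, relatedness and surgery date are already collected, and no event is lost. The downsides are fewer events in the late table and, in the related-only version, reliance on investigator attribution. The all-causality version beside it offsets the second.
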